5.2 Exclusion criteria

Patients must not enter the study if any of the following exclusion criteria are fulfilled:

1. Age <18 years of age.
2. Failure to obtain informed consent.
3. Clinical judgment by the investigator that the patient should not participate in the study (reasons will be recorded in the screening log).
4. HIV infection in association with a last known CD4 count of $\leq 50/\text{mm}^3$, cytomegalovirus, disseminated mycobacterium avium complex disease, toxoplasmosis, or progressive multifocal leukoencephalopathy.
5. Moribund, and death is considered imminent within 24 hours.
6. Inability to maintain a mean arterial pressure ≥ 50 mmHg when measured via an arterial line and/or systolic blood pressure (BP) > 70 mmHg for at least 1 hour prior to screening despite the presence of vasopressors and iv fluids.
7. Patient is not expected to survive 90 days because of underlying medical condition, such as poorly controlled neoplasm (eg, Stage III or IV cancer). [Appendix J](#) contains the specific exclusion criteria for malignancies (contact the CCC for guidance).
8. Patient's family is not committed to aggressive management of the patient's condition, or the combination of sepsis and underlying illness makes it unlikely that life support will be maintained.

9. Haemopoietic and lymphoreticular malignancies, unless in remission (patients in remission must have completed induction and consolidation therapy before provision of written informed consent for the study).
10. Patients undergoing active radiation or chemotherapy treatment for any type of malignancy. Hormonal manipulation therapies for breast and prostate malignancies are permitted.
11. Any stem cell, organ or bone marrow transplant within the past 6 months prior to provision of informed consent for study.
12. High dose steroids (eg, >40 mg or 0.5 mg/kg prednisone or a steroid with equivalent activity, daily for >7 days) within 1 month before provision of written informed consent for the study (See [Appendix I](#)).
13. Granulocytopenia, not due to sepsis, as evidenced by leukocyte absolute neutrophil count <500 per μ L.
14. Patients with biopsy proven cirrhosis and documented portal hypertension; episodes of past upper gastrointestinal bleeding attributed to portal hypertension; or prior episodes of hepatic failure/encephalopathy/coma or patients who appear to be Childs-Pugh Class C.
15. Second or third degree burns involving more than 30% of body surface within 5 days before provision of written informed consent for the study.
16. Conditions resulting in a New York Heart Association Class IV functional status.
17. Females of child bearing potential who do not have a negative pregnancy test (serum) at screening (patients may be entered into the study on the basis of a negative urine pregnancy test, pending the results of a serum pregnancy test; if the serum pregnancy test is positive, the patient must be discontinued from study treatment). Post-partum patients who have a persistent positive pregnancy test (human chorionic gonadotropin [HCG] values have not had time to decrease) will be allowed in the study. Females who are lactating and insist on breast feeding within 5 days of the last dose of study drug if their sepsis resolves.
18. Potential intolerance to AZD9773 drug product:
 - Any history of hypersensitivity reaction to sheep products, latex, papain or papaya, chymopapain, eg, meat tenderisers or contact lens cleaning solution containing papain or chymopapain.
 - Previously administered antivenom manufactured using ovine serum, digoxin immune Fab (DigiFab™, DIGIBIND®) crotalidae polyvalent immune Fab (ovine) (CroFab™), or other sheep-derived product.

19. Treatment with anti-TNF antibodies (eg, infliximab [REMICADE[®], Centocor], adalimumab [Humira[®], Abbott Laboratories], etanercept [Enbrel[®], Immunex]) or IL-1 Receptor Antagonist (Kineret) within last 8 weeks.
20. Enrolment in an interventional experimental protocol involving investigational drug or a medical device within 60 days before provision of written informed consent for the study or within five half-lives of the study drug, whichever is longer (Co-enrolment in process of care trials or comparative trials of approved products will be allowed if the protocol has been approved in advance by the sponsor, as long as the co-enrolment does not violate participation in the other protocol).
21. Deep-seated fungal infection (eg, histoplasmosis, cryptococcal meningitis and aspergillosis). Superficial fungal infections are not excluded (eg, tinea pedis, yeast infections [eg, oral thrush, candida dermatitis] limited to skin).
22. Active tuberculosis (documented, or strong clinical suspicion or patients receiving active treatment for tuberculosis).
23. Severe chronic respiratory disease (ie, present before the onset of the current episode of severe sepsis and/or septic shock) that would prevent weaning from mechanical ventilation. Examples of severe disease may include:
 - Chronic hypercarbia ($\text{PaCO}_2 > 45$ mmHg) and /or chronic hypoxemia (partial pressure of arterial oxygen [PaO_2] < 55 mmHg) on fraction of inspired oxygen ($\text{FiO}_2 = 0.21$), OR
 - Hospitalisation for respiratory failure ($\text{PaCO}_2 > 50$ mmHg or $\text{PaO}_2 < 55$ mmHg or oxygen saturation [O_2 Sat] $< 88\%$ on $\text{FiO}_2 = 0.21$) within last 6 months, or chronic use of home ventilation, OR
 - Unable to climb stairs or perform household duties due to chronic restrictive, obstructive, neuromuscular, chest wall or pulmonary vascular disease resulting in severe exercise restriction, OR
 - Use of continuous home oxygen prior to hospital admission. Sleep apnoea treated with continuous positive airway pressure or biphasic positive airway pressure oxygen during sleep is acceptable.
24. End-stage neuromuscular disorders that impair the patient's ability to ventilate spontaneously (eg, amyotrophic lateral sclerosis).
25. Patients with complete quadriplegia (traumatic or otherwise). All other patients not ambulatory (eg, chronically bed-bound, failure to thrive, cachexia) prior to onset of sepsis will need to be reviewed and approved by the CCC prior to enrolment.

26. Patients with cardiac arrest requiring cardiopulmonary resuscitation within the past 30 days. If the patient has documented complete neurological recovery or if the cardiopulmonary resuscitation was brief and associated with intubation the patient will not be excluded. The patient must be able to follow commands post-arrest.
27. Involvement in the planning and/or conduct of the study (applies to AstraZeneca and PAREXEL staff and/or staff at the study site).
28. Previous randomisation of treatment in the present study or any other AZD9773 study.

Patients must not enter the genetic and/or biomarker portion of the study if the following exclusion criterion is fulfilled

1. Patients who have received a whole blood transfusion within 120 days of the date of genetic sample collection.

5.3 Procedures for handling incorrectly included patients

Patients that do not meet the inclusion/exclusion criteria for the study should not, under any circumstances, be randomised into the study - there are no exceptions to this rule.

If any randomised patients are subsequently found to have not met the inclusion/exclusion criteria then a discussion must occur between the CCC, the Medical Monitor, the AstraZeneca Study Team Physician and the investigator regarding whether to continue or discontinue the patient from the study treatment. Such patients should only be discontinued from treatment if there are safety concerns. However, as this study is including an Intention-to-treat (ITT) analysis, any such patient must be followed up according to the study plan. Decisions must be appropriately documented by the CCC.

5.4 Withdrawal of patients

5.4.1 Criteria for discontinuation from the study treatment

Patients may be discontinued from study treatment at any time. Specific reasons for discontinuing a patient from study treatment are:

- Voluntary discontinuation by the patient who is at any time free to discontinue study treatment, without prejudice to further treatment (incapacitated patients may be withdrawn from study treatment by their legally authorised representative).
- AEs (eg, risk to patients as judged by the investigator and/or IDMC, CCC, PAREXEL or AstraZeneca).
- Severe non-compliance to protocol as judged by the investigator and/or CCC, PAREXEL, or AstraZeneca.
- See Section 5.3 for the procedures for handling incorrectly enrolled patients.

- Patient discharged from an adequately monitored setting.
- Positive pregnancy test (except for post-partum).
- Severe reaction to study drug infusion, or progressive, moderate reaction continuing to worsen, or the patient is refractory (eg, moderate reaction which does not respond to treatment) or at the discretion of the investigator ([Appendix D](#)) or study drug is not tolerated.
- Treatment is unblinded by the site investigator or designee.
- Need for immunosuppressant drugs and/or anti-TNF antibodies other than study drug. In the event of the need for these medications, the patient will be discontinued from study treatment but details of the medications (drug name, start date and time, dose, route of administration, stop date and time) will be collected for 28 days from the start of study drug (see Section [6.5.2](#) on concomitant medications).
- Dosing can be discontinued before all 10 doses are administered if the patient improves and maintains improvement for 24 hours (see Section [4.1](#)).

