13.3 Methods of statistical analyses

13.3.1 Demographics, baseline characteristics, and concomitant medications

Demographic data, medical history, surgical history, Charlson Comorbidity Scale, physical examination (including dermal examination and lung auscultation), and key concomitant medications will be summarised. Concomitant medications will be coded using the AstraZeneca Drug Dictionary.

Patients who have to discontinue study treatment due to the administration of immunosuppressant medications, corticosteroids other than for adrenal replacement therapy, and anti-TNF antibodies during Days 1 to 6 will be summarised by treatment group.

Baseline disease characteristics including APACHE II Score, Glasgow Coma Score, TNF α , time of initial antibiotic dose relative to the qualifying organ failure and the number of patients with shock, on a ventilator, on vasopressors, with a positive culture or with renal impairment will also be summarised.

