(b) Recommended management in the event of a reaction to drug administration.

- Assess severity: mild, moderate, or severe (see Section IV for details).
- Stop infusion and consider treatment options (see Section V for details).
 - Include: observation, acetaminophen, diphenhydramine, steroids, epinephrine, fluids, albuterol, pressors, airway management and other measures in line with accepted medical practice as deemed necessary by the treating physician eg, iv histamine H2 receptor blockers.
- Monitoring (see Section VI).
- Consider restarting infusion after appropriate management and stabilisation or improvement in symptoms.
- Completion of infusion reaction adverse event (AE) form.

III Post infusion

(a) Monitoring

- A minimum of lung auscultation and dermal examination (eg, for oedema, urticaria, rash) should be done after the infusion is complete. In the event of an infusion of hypersensitivity reaction (as evidenced by a causal change in BP, skin or lung examination), an additional full physical examination should be performed and changes (skin, lung, physical examination and BP) should be recorded in the electronic Case Report Form.

- Laboratory parameter measurements
 - At timepoints according to the study plan (Table 1 of protocol).
 - Serum tryptase, IgE and quantitative eosinophil count, 20 to 60 minutes post suspected infusion or hypersensitivity reaction and repeated on blood draw at Day 29.
- (b) Classifying any infusion reactions
 - Timing
 - Early (onset during infusion or within 1 to 4 hours after infusion).
 - Intermediate (4 to 24 hours after end of infusion).
 - Delayed (onset from 24 hours to 4 weeks after end of infusion).
 - Severity (see Section IV).
 - Type
 - Timing: early, late or intermediate.
 - Hypersensitivity reaction versus infusion reaction.
 - (i) Any adverse reaction, which occurs within the dosing time, is potentially an infusion reaction.
 - (ii) A clinical picture of chills, rigors, fever, myalgia, wheeze, cough dyspnoea, altered vital signs or combination of signs and symptoms consistent with allergic phenomena/infusion reaction. Differentiation will be in immune system activation as evidenced by blood parameters eg, tryptase rise and response to slowing the rate of infusion: this will not affect a true hypersensitivity reaction.
- Investigate relationship of frequency, severity to:
 - History (eg, atopy, asthma, drug allergies).
 - Infusion rate.
 - Infusion concentration.
 - Infusion dose.
 - Infusion number.

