
- Laboratory parameters (eg, total or specific IgE, complement, immune complex, tryptase) to help determine aetiology.
 - Response to treatment.
- (c) Re-treatment (after the full 5-day course, patients should not be re-treated)
- (d) Information to patients
- When the blind is broken, tell a patient whether they had active or placebo. For those who have had active treatment say, “In future if you require any treatment derived from sheep you should inform your physician that you have received sheep derived products as a treatment for sepsis.”

IV Classifying infusion reactions

- (a) Severe; new onset, temporally-related (**any one or more of the following**):
- Hypo/hypertension (eg, systolic BP [SBP] change >40 mmHg; absolute SBP <80 or >180 mmHg).
 - Tachy/bradycardia (eg, heart rate [HR] change >20 beats per minute [bpm] or absolute HR >120 bpm or <60 bpm).
 - Tachy/bradypnoea (eg, respiratory rate [RR] change >10/min).
 - Hyperthermia (eg, temperature >40°C).
 - Evidence of significant angioedema (eg, requiring intubation or treatment) or bronchospasm (eg, associated hypoxia or necessitating change in vent settings or treatment).
- (b) Moderate; new onset, temporally-related (**any one or more of the following**):
- SBP change of 20 to 40 mmHg.
 - HR change of 10 to 20 bpm.
 - RR change of 4 to 10/min.
 - Temperature increase, but <40°C.
 - Evidence of non-clinically significant angioedema or bronchospasm.
 - Rash/urticaria/peripheral oedema requiring treatment.
 - Vomiting requiring treatment.

- Symptoms (eg, pruritis, chills, myalgias, arthralgias) or other effects requiring treatment.
- (c) Mild includes any other new onset, temporally-related symptoms or signs consistent with hypersensitivity reactions such as rash, wheeze or urticaria

V Management of suspected infusion reactions

This section includes but should not be limited to the following measures:

Early and intermediate reactions

- (a) Stop or decrease infusion
 - Stop if severe (see Section IV), progressive (continuing to worsen), refractory (eg, moderate reaction which does not respond to treatment) or at discretion of investigator.
 - For other events, infusion will be stopped or slowed
 - If the infusion is not tolerated and there is no previously tolerated rate the investigator may prolong the infusion time to twice the initially planned infusion time for that timepoint (if warranted the infusion time can be doubled again to increase tolerability).

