 - If the infusion is stopped or decreased, wait until signs/symptoms have been stable for 15 minutes prior to restarting or increasing rate.
 - Wait 15 minutes and consider restarting infusion at half the initial rate (equivalent to doubling the time planned for the infusion).
- (b) Treatment options
 - Signs/symptoms including but not limited to:
 - Hypotension (fluids, pressors).
 - Bronchospasm (inhaled albuterol, antihistamines, epinephrine, steroids).
 - Angioedema (intubation/airway management, antihistamines, epinephrine, steroids).
 - Hyperthermia (cooling measures, acetaminophen, antihistamines, steroids, epinephrine).
 - Rash/urticaria (antihistamines, steroids, epinephrine).
 - Vomiting (antiemetics).

- Symptoms such as pruritis, chills, myalgias, arthralgias (acetaminophen, antihistamines, steroids, epinephrine).
- Treatment/drug, suggested doses including, but not limited to:
 - Epinephrine (1:1000 0.1 to 0.5 mL subcutaneously; repeat as necessary).
 - Diphenhydramine (25 to 50 mg iv; repeat as necessary).
 - Albuterol/salbutamol (0.5 mL of 0.5% solution, nebulised; repeat as necessary).
 - Methylprednisolone (20 to 40 mg iv).
 - Acetaminophen (625 mg orally if oral route can be tolerated).
 - Pressors (eg, dopamine, epinephrine, norepinephrine to maintain organ perfusion, SBP >90 mmHg, mean arterial pressure >70 mmHg).
 - Oxygen to keep oxygen saturation >92%; airway and ventilation setting adjustment to maintain normal ventilation.
 - iv fluids (500 to 1000 mL/hour to help maintain adequate perfusion).

Delayed infusion reactions

- Investigator discretion with following suggested treatment options:
 - Acetaminophen.
 - Steroids (orally, or iv if severe).
 - Antihistamines (orally, or iv if severe).
 - Monitoring; human anti-sheep antibodies, auto-antibody screen, routine laboratory measurements and total IgE.

VI Monitoring of suspected infusion reactions

- (a) Standard medical monitoring for an ICU setting to include at least the following:
 - Vital signs every 2 minutes until stable.
 - Clinical examination every 5 minutes until stable.
 - Laboratory parameter measurements to consider:

- Serum tryptase, IgE and quantitative eosinophil count, 20 to 60 minutes post suspected infusion or hypersensitivity reaction and repeated on blood draw at Day 29.

THIS IS A PRINTED COPY OF AN ELECTRONIC DOCUMENT. PLEASE CHECK ITS VALIDITY BEFORE USE.

Clinical Study Protocol Appendix E

Drug Substance	AZD9773
Study Code	D0620C00003

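### Section 5.4.1 lists a severe infusion reaction as a reason to end study treatment, while Appendix D lets a restart be considered with no limit by severity

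*Protocol*

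**What the plan says.** Section 5.4.1 opens permissively ("Patients may be discontinued from study treatment at any time") and then lists reasons. One bullet reads "Severe reaction to study drug infusion, or progressive, moderate reaction continuing to worsen, or the patient is refractory". The same bullet goes on to investigator discretion, with a reference to Appendix D, and to study drug that is not tolerated. Section 6.4.2 also sends sites to Appendix D for guidance on tolerability.

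Appendix D V(a) uses nearly the same list, but as the trigger for halting the infusion: "Stop if severe (see Section IV), progressive (continuing to worsen), refractory (eg, moderate reaction which does not respond to treatment". For the remaining reactions it says "For other events, infusion will be stopped or slowed". It lets the investigator lengthen an infusion that is not tolerated when no tolerated rate is known. Its restart text follows: "If the infusion is stopped or decreased, wait until signs/symptoms have been stable for 15 minutes prior to restarting or increasing rate", and "Wait 15 minutes and consider restarting infusion at half the initial rate".

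Appendix D II(b) gives one sequence for any reaction during an infusion. The site grades it as mild, moderate or severe, stops the infusion, treats, monitors, and then: "Consider restarting infusion after appropriate management and stabilisation or improvement in symptoms".

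On steroids, Section 13.3.1 plans a summary for the treatment period that covers "Patients who have to discontinue study treatment due to the administration of immunosuppressant medications, corticosteroids other than for adrenal replacement therapy". Anti-TNF agents are the third class in that list. Appendix D V(b) offers methylprednisolone among the suggested treatments for a reaction.

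**The concern.** Both passages address the same event. Section 5.4.1 deals with the whole course of study treatment and Appendix D with the infusion in progress, but a patient whose study treatment has ended cannot also have the infusion restarted. No text says that the restart steps leave out the reactions named in 5.4.1, or that 5.4.1 takes effect only after a restart has failed.

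The first thing at stake is a patient-safety rule: re-exposure to a sheep-derived protein after a severe reaction, at about 100 planned centres. The second is how the safety tables read. Sections 13.3.9.2 and 13.3.9.3 count adverse events that lead to withdrawal from study drug. If centres apply different passages, that count mixes the severity of reactions with local interpretation.

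**Working it through.** The point is textual and the plan gives no figure to reproduce, so the passages are compared event by event.

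1. **Severe reaction that settles.** 5.4.1 lists it as a reason to end study treatment. Appendix D II(b) grades severe reactions explicitly and reaches the restart step with no exception. Appendix D V(a) stops the infusion and then gives a restart condition for an infusion that has been stopped. Here the passages conflict.

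2. **Progressive or refractory reaction.** 5.4.1 lists both. The V(a) restart condition is 15 minutes of stability, which a reaction that is still worsening or not responding does not meet. There is no conflict while the reaction persists; one arises only if it later settles.

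3. **Study drug or infusion not tolerated.** 5.4.1 lists lack of tolerability as a reason to end treatment. V(a) allows the infusion time to be doubled, and doubled again if warranted. No text says when slowing is the response and when treatment ends.

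4. **Later doses.** Appendix D covers restarting the current infusion. It does not say whether the remaining maintenance doses may follow a severe reaction.

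5. **Corticosteroid given for a reaction.** Section 13.3.1 speaks of patients who have to stop because of non-replacement corticosteroids. Sections 5.4.1, 6.1 and 6.5.2 name immunosuppressants and anti-TNF antibodies but not corticosteroids. Section 6.5.2 also permits other medication needed for the patient's safety. Section 13.2.3 takes its list of prohibited medications from 6.5.2. The documents therefore do not settle whether such a patient stops treatment or leaves the per-protocol population, which Section 13.1 uses for all efficacy data.

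**Outer limit per patient.** The dose regimens in Section 4.1 bound what can turn on the choice of passage when the reaction occurs during the loading dose:

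- Dose arm 1: at most 250 units/kg if treatment ends, against 250 + 9 × 50 = 700 units/kg if the infusion is completed and all nine maintenance doses follow.
- Dose arm 2: at most 500 units/kg, against 500 + 9 × 100 = 1400 units/kg.

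These are maxima, not expected differences. The upper figures assume that every later dose is given, which Appendix D neither states nor rules out.

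**The case against.** The best defence is that the wording is discretionary. 5.4.1 opens with permission to discontinue, whereas the protocol uses mandatory verbs where it means them, as for a positive serum pregnancy test or prohibited immunosuppressants. Appendix D is recommended management, speaks of considering a restart, and defers to the investigator's judgement of the patient's best interest. This stands in part. A reader might infer that sites will act in opposite ways; the text supports only that they could. Discretion does not say which passage governs, however, and each of the two is written as guidance on the same event.

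A second defence is that the restart bullets in V(a) belong only under the line on other events, with the nesting lost when the text was read from PDF. On that reading V(a) agrees with 5.4.1, and the possibility cannot be excluded. It does not clear II(b), which grades severe reactions and reaches the restart step without any limit. II(b) does refer to Section V for details, but on treatment options.

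Two stronger readings fail. One is that inconsistent stopping would bias the comparison between active drug and placebo. Appendix D IV calls a reaction severe on a single new, temporally related sign, for example a heart-rate change above 20 bpm or a systolic change above 40 mmHg. Placebo patients with septic shock can meet that. In addition, Section 5.4.4 keeps patients in follow-up after study drug stops, and the ITT population retains all randomised patients. The other is that a dose of methylprednisolone for a reaction takes the patient off study drug. Section 13.3.1 describes a summary, and the corticosteroid entry in Appendix I is an eligibility limit on use before consent. Neither is a stopping rule.

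**Conclusion.** The conflict is real but narrow. It is firm between 5.4.1 and Appendix D II(b) for a severe reaction that resolves, and it is present on lack of tolerability between 5.4.1 and V(a). It is possible, depending on bullet nesting, for the restart text in V(a). Sites could handle re-exposure differently, and summaries of withdrawal due to adverse events could partly reflect the passage followed.

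The number of patients affected is unknown. The documents give no rate of severe infusion reactions, and Sections 2.1.4 and 2.3 report that higher doses were well tolerated in the Phase IIa study. No effect on the primary comparison is shown. The point matters because it concerns a safety rule that sites must apply within minutes. The corticosteroid mismatch is secondary: Section 13.3.1 presupposes a rule that appears nowhere else. No view is taken here on which clinical rule is right.

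**What to change.** Reconcile Section 5.4.1 with Appendix D II(b) and V(a) by amendment. One passage should state, for each severity grade and for an infusion that is not tolerated, whether the current infusion may be restarted or continued and whether later doses may be given. The other passages should refer to it. The sponsor's physicians decide the content of the rule.

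In the same amendment, state whether a corticosteroid given to treat a reaction is a reason to stop study treatment and whether it excludes the patient from the per-protocol population. Then make Sections 5.4.1, 6.1, 6.5.2, 13.2.3 and 13.3.1 and Appendix D agree.

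The cost is one protocol amendment and a memo to sites, with no added patients or procedures.
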